# **1.2 Document History**

Document History	Date	Protocol No. and Version No.	Valid Range
Initial version	20 APR 2020	BNT162-03-CN, Version 1.0	China
Initial submitted version	20 MAY 2020	BNT162-03, Version 1.0	China
Amendment 1	10 JUL 2020	BNT162-03, Version 2.0	China
Amendment 2	26 JUL 2020	BNT162-03, Version 2.1	China
Amendment 3	5 AUG 2020	BNT162-03, Version 3.0	China

#### 2.0 TRIAL SUMMARY

BioNTech RNA Pharmaceuticals GmbH	Product Name:							
[name],	SARS-CoV-2 mRNA Vaccine (BNT162b1)							
[name]								
Trial Title: Safety and Immunogenicity of SARS-CoV-2 mRNA Vaccine (BNT162b1) in Chinese Healthy Subjects: A Phase I, Randomized, Placebo-controlled, Observer-blind Study								
IND No.: 2020L00032/ 2020L00033	EudraCT No.: NA							
Study Identifier: BNT162-03 Phase: I	Trial Blinding Schema: Observer-blind							

# **Study Identifier:** BNT162-03 **Background and Rationale:**

SARS-CoV-2 is a single-stranded positive-sense ribonucleic acid (RNA) virus which belongs to the coronavirus family that presents about 78% of structural similarities with other members of the coronavirus, including SARS virus. Coronaviruses are a large family of viruses that are common in many different species of animals, including camels, cattle, cats, and bats. It is rarely for animal coronaviruses to infect people and then spread among infected people just like SARS-CoV-2.

SARS-CoV-2 was discovered in January 2020 in Wuhan. The first human disease cases were reported in December 2019 in China. The virus circulated in areas of over 200 countries worldwide, and was considered Acute Respiratory disease syndrome (COVID-19) with mild to severe symptoms. The primary mode of transmission of SARS-CoV-2 is person-to-person contact through respiratory droplets. Patients with mild or asymptomatic infections may account for 60% of all infected patients. Some clinical manifestations include, but are not limited to, fever, cough, and diarrhea. [2,3]

Despite mild clinical symptoms in most adults, SARS-CoV-2 infection over 65 years old has been associated with serious outcomes. The severity of the disease is related to the attacks of autoimmunity on pulmonary alveoli. Since the beginning of these outbreaks and up to mid-May 2020, there has been more than 4,580,000 confirmed COVID-19 associated with SARS-CoV-2 infection with over 310,000 deaths in over 200 countries, areas, or territories worldwide. [4]

SARS-CoV-2 is a respiratory virus that can cause disease of the respiratory system. The overall incidence of SARS-CoV-2-associated COVID-19 is unknown currently. In the epidemic curve up to January 4, 2020, the epidemic growth rate was 0.10 per day (95% CI, 0.050 to 0.16) and the doubling time was 7.4 days (95% CI, 4.2 to 14). Using the serial interval distribution above, we estimated that R0 was 2.2 (95% CI, 1.4 to 3.9) [3].

No specific antiviral treatment is available for SARS-CoV-2 infections and no vaccine against SARS-CoV-2 is currently available. As the disease is self-limiting, treatment for uncomplicated COVID-19 infection is supportive and focuses on symptoms. The main recommendations to prevent outbreaks are through social distancing (avoiding person-to-person contact transmission), and personal protective equipment (PPE) measures.

The risk of infection with SARS-CoV-2 is increasing given that the spread of SARS-CoV-2 is rapid and intense in over 200 countries, areas, or territories. SARS-CoV-2 has posed a challenging situation for health, public and economic sectors of affected countries.

The World Health Organization (WHO) declared on 30 January 2020 the SARS-CoV-2 outbreak as a Public Health Emergency of International Concern (PHEIC) and recommended to focus the research on the causal association of SARS-CoV-2 infection. Considering the spread to more new countries, this novel coronavirus disease COVID-19 outbreak was assessed as very high of global risk level on February 28 2020, and was declared as a pandemic by the WHO on March 11 2020. Considering the conclusive associations between SARS-CoV-2 infections and severe acute respiratory syndrome, the development of a vaccine that can provide protection is crucial for countries where the epidemic is expected to arrive and/or persist, as well as in countries in which the

virus has not yet been epidemic. In order to address the urgent medical need and in anticipation of possible outbreaks with rapid onsets, the sponsor has initiated the development of a SARS-CoV-2 mRNA vaccine (BNT162b1), for use in endemic areas and non-endemic areas for prevention of SARS-CoV-2 associated illness of any severity and/or infection.

The urgent engagement in the efforts to investigate, make available safe and effective SARS-CoV-2 interventions are needed to assist in the control of the outbreak. Given the severity of the situation, time to vaccine development was an important aspect of the highly unmet needs. In response to this need, an accelerated vaccine development effort was initiated.

Two Phase I/II clinical studies of BNT162b1 are currently being conducted in Germany and the United States; at the same time, the immunogenicity, repeated dose toxicology study and viral challenge study are conducted in BALB/c mice in accordance with Good Laboratory Practice (GLP) to continuously analyze the efficacy and safety of BNT162b1 at animal level and human body level. Interim Report of the United States Phase I/II clinical study has been published. Results of data analyses for pre-clinical studies and clinical studies will be provided by continuously updating in the Investigator's Brochure (IB). The clinical studies conducted in Germany and the United States are first-in-human trials, so dose escalation mode is adopted and sentinel subjects are added for both. The maximum dose examined in these two studies is 100µg, and the safety result shows that the local reaction of vaccination site and systemic event are dose-dependent which is mostly mild to moderate with short duration, reactions after two vaccinations are similar, and reaction is slightly less in elderly group; immunogenicity result shows that serum RBD specific IgG antibody concentration and SARS-CoV-2 neutralizing antibody titer escalate with dose level and increase after booster vaccination. The geometric mean neutralizing titer is 1.8 to 2.8 times that of a group of COVID-19 human serum during recovery period. Above results will support the further evaluation of the mRNA candidate vaccine. Currently, the optimal dose range is predicted as 10~30 µg according to safety and efficacy data of foreign subjects. Since the preliminary safety and immunology data are obtained, and clinical studies conducted in Germany and the United States will continue to support studies in China, so China plans to conduct bridging trial to confirm foreign study results among Chinese subjects.

BNT162-03 is a phase I, dose confirmation study in China, which adopts a parallel two-dose cohort design in adult healthy subjects (adult group) and elderly healthy subjects (senior group); and the trial in adult group is conducted firstly and followed by the trial in the elderly group. And the study is intended to confirm that the response (safety/immunogenicity) seen in foreign subjects is comparable to that in Chinese subjects. Healthy adults who are  $\ge 18$  years old and  $\le 55$  years old will be enrolled in the adult group and healthy elderly subjects who are  $\ge$ 65 years old and  $\le$ 85 years old will be enrolled in the elderly group. To ensure the enrollment of healthy subjects, screening tests (hematology, biochemistry, and urinalysis) will be performed prior to vaccine/placebo vaccination. In each age group of subjects, the trial will be conducted by the parallel two-dose and placebo cohort allocation. The design of this study, including the selection of two optimal dose levels referred to the safety and immunogenicity data from the ongoing or completed foreign studies of BNT162b1. In this study, a Safety Review Committee (SRC) will be comprised of investigators, Fosun medical representative and medical monitor, and SRC will review the safety data in a blinded manner. SRC will review the available safety and tolerability data of all subjects in a dose cohort (including at least safety laboratory test results and safety events collected from diary cards within 14 days after the prime vaccination) before starting the boost vaccination for each cohort to suggest whether the boost vaccination of BNT162b1 vaccine can be conducted. The study will also set up an Independent Data Monitoring Committee (IDMC) to conduct overall supervision. The IDMC is required to review the unblinded data when a significant event or risk occurs in the study that might cause the study to be suspended.

Due to the ongoing threat of SARS-CoV-2 disease and the urgent need of a vaccine, this study will be accelerated to assess the bridging data for BNT162b1, in addition to confirm that the response (safety/immunogenicity) seen in foreign subjects is comparable to that observed in Chinese subjects.

Placebo serves as the control for the study vaccine and in the absence of effective treatment or prevention for COVID-19, the use of placebo in this trial is justified. Based on the different physical appearance of the

investigational vaccine compared to the saline solution placebo that will be selected, an independent non-blind team is adopted in this study for blinding subjects and observers.

All enrolled subjects will receive two doses of either SARS-CoV-2 vaccine (BNT162b1) or placebo intramuscularly (IM) on Day 1 and on Day 22. The objective of the study BNT162-03 is to assess the safety and immunogenicity of BNT162b1 in the Chinese healthy subjects.

The primary rationale for selection of the vaccine dose levels can be summarized as follows:

Based on the clinical data from the overseas clinical studies, and the non-clinical data of the RNA components (modRNA), with other liposomes or in conjunction with the lipid nanoparticles as will be tested clinically in this trial, we expect that doses in the 1 to 5 μg range will be immunogenic and induce neutralizing antibodies. The dose range of 1~100 μg has been identified in foreign subjects, based on safety and efficacy data. Accordingly, a degree of reactogenicity is anticipated with BNT162b1 with mild or moderate local or systemic reactions common amongst subjects.

Two predicted optimal doses are selected according to the safety and immunogenicity data of global clinical trials in Germany and the United States as available at present to confirm the comparability of safety and efficacy for BNT162b1 in China.

- The low-dose level (10 μg);
- The high-dose level (30 μg);

The trial will be conducted in accordance with the protocol, the International Council for Harmonization of Technical Requirements for Pharmaceuticals (ICH) GCP Guidelines and applicable regulatory requirements.

[figure not shown]

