  of titer detection, the positive conversion is defined as the antibody titer reaching at least 4 times of the lower
  limit.

Safety analysis: Within 14 days after each vaccination (Including the day of vaccination of vaccine/placebo), by collecting soliciting AE, including local reactions (Vaccination site: pain/tenderness, erythema/redness, induration/swelling) and general reactions (nausea, vomiting, diarrhea, headache, fatigue/tiredness, myalgia, arthralgia, chills loss of appetite, malaise and fever), to evaluate reactogenicity. In addition, body temperature (axillary) as indicator of reactogenicity will be collected (with fever defined as axillary temperature  $\geq 37.3^{\circ}$ C, oral temperature  $\geq 38.0^{\circ}$ C).

For each solicited reaction, including fever, the percentage of subjects will be summarized by event severity for each day within 14 days after each vaccine/placebo vaccination and overall.

All AEs and SAEs will be coded using the Medical Dictionary for Regulatory Activities (MedDRA version 23.0) and summarized by system organ class (SOC) and preferred term (PT) for each group (BNT162b1 and placebo) including aggravation after vaccination and new medical conditions.

Safety summaries will be provided by different age groups and different dose cohorts/placebo groups.

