## 4.2.4.1 Safety summary

According to the periodic summary of the United States Phase I/II clinical study, pain at the injection site was the most common local reaction within 7 days of the first dose and the second

dose of vaccine; after the first vaccination, probability of pain in 10  $\mu g$  group was 58.3% (7/12), in 30  $\mu g$  group and 100  $\mu g$  group were 100.0% (12/12), and in placebo group was 22.2% (2/9). After the second vaccination, there were 83.3% and 100.0% of subjects got pain respectively in the dose level of 10  $\mu g$  and 30  $\mu g$ , while 16.7% subjects in placebo group got pain. All local reactions were mild or moderate except the 100  $\mu g$  group reported severe pain after inoculation of BNT162b1.

Within 7 days of each vaccination, the most common systemic events reported in BNT162b1 and placebo groups were mild to moderate fatigue and headache. Fatigue and headache were more common in BNT162b1 than that in placebo group. Furthermore, chills, muscle pain and joint pain were reported in the BNT162b1 group, but not in the placebo group. Systemic events increased with dose levels, and there were an increased number of subjects reporting systemic events after the second vaccination (10  $\mu$ g and 30  $\mu$ g groups). After the first vaccination, there were 8.3% (1/12) of subjects respectively in 10  $\mu$ g group and 30  $\mu$ g group, and 50.0% (6/12) of subjects in 100  $\mu$ g group got fever (defined as  $\geq$ 38.0° C). Based on the reactogenicity reported after the first dose of 100  $\mu$ g and the second dose of 30  $\mu$ g, subjects initially received 100  $\mu$ g of vaccination will no longer receive the second vaccination. After the second vaccination, 8.3% (1/12) of subjects in 10  $\mu$ g group and 75.0% (9/12) of subjects in 30  $\mu$ g group got fever  $\geq$ 38.0° C. The fever usually got resolved within 1 day of onset. There was no systemic event or fever of grade 4. Most local reactions and systemic events peaked 2 days after vaccination and resolved at day 7.

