According to the periodic summary of the United States Phase I/ II clinical study, geometric mean concentration (GMC) of RBD specific IgG was 534-1,778 U/mL 21 days after prime vaccination. In contrast, RBD specific IgG GMC was 602 U/mL in 38 samples of sarS-COV-2 infection /COVID-19 convalescent human serum taken from patients aged 18-83 years old and at least 14 days after PCR confirmation. 7 days after the second vaccination (at dose levels of 10 μg and 30 μg), the GMC of RBD specific IgG antibody increased to 4,813-27,872 U/mL. 21 days after prime vaccination, RBD specific antibody concentrations were not increased in subjects who received the first dose of 100 μg BNT162b1. In subjects receiving doses of 10 μg and 30 μg BNT162b1, high concentrations of RBD specific antibodies persisted until the last time point so far assessed (day 35 of the trial, 14 days after the second vaccination). These RBD-binding antibodies were present at concentrations of 5,880-16,166 U/mL.

For all dose groups, a moderate increase in SARS-COV-2 neutralizing geometric mean titer (GMT) was observed 21 days after the first vaccination. 7 days after the second dose of 10 µg or 30 µg vaccine, the GMT of serum neutralizing antibody was significantly increased to 168-267, while the GMT of human serum during recovery was 94.

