# 5.1.1 Primary objective

• To assess the safety and tolerability profiles of BNT162b1 prime/boost (P/B) immunization given 21 days apart from different dosages in SARS-CoV-2 naïve Chinese healthy subjects through 28 days after boost vaccination.

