5.1 Immunogenicity Endpoints

The Immunogenicy endpoints at Day 7, Day 21 after prime immunization, at Day 7, Day 21 after boost immunization, Month 3, 6 and 12 after prime immunization are defined as follows:

- (1) Geometric mean titer (GMT) of anti-S1 IgG antibody.
- (2) GMT of anti-RBD IgG antibody.
- (3) GMT of SARS-CoV-2 neutralizing antibody (based on true virus' SARS-CoV-2 neutralizing test).
- (4) Geometric mean fold increase (GMFI) in anti-S1 IgG antibody, as compared to baseline.
- (5) GMFI in anti- RBD IgG antibody, as compared to baseline.
- (6) GMFI in SARS-CoV-2 neutralizing antibody, as compared to baseline.
- (7) Seroconversion rate (SCR) of anti-S1 IgG antibody. Seronegative is defined as titers below the starting dilution (1:100) and assigned a titer of 50. Seroconversion after vaccination is defined as a minimum of 4-fold increase of antibody titers, as compared to baseline.
- (8) SCR of anti-RBD IgG antibody. Seronegative is defined as titers below the starting dilution (1:100) and assigned a titer of 50. Seroconversion after vaccination is defined as a minimum of 4-fold increase of antibody titers, as compared to baseline.
- (9) SCR of SARS-CoV-2 neutralizing antibody. Seronegative is defined as titers below the starting dilution (1:10) and assigned a titer of 5. Seroconversion after vaccination is defined as a minimum of 4-fold increase of antibody titers, as compared to baseline.

The immunogencity endpoints at Month 3, 6 and 12 after prime imunizaton are to assess the immunogencity persisence of BNT162b1.

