- > TEAEs leading to discontinuation by SOC and PT
- Related TEAEs leading to discontinuation by SOC and PT
- Unrelated TEAEs leading to discontinuation by SOC and PT
- ➢ AESIs by SOC and PT
- Related AESIs by SOC and PT
- Unrelated AESIs by SOC and PT
- ➢ TESAEs by SOC and PT
- Related TESAEs by SOC and PT
- > Unrelated TESAEs by SOC and PT

The DLT AE and related DLT AE will be summaried by group. The distribution of severity, injection stage, occurrence will be provided for TEAEs and related TEAEs. The episodes of AEs, number and percentage of subjects with TEAEs will be summarized by worst grade by PT nested within SOC.

For each solicited reaction (including fever), the number and percentage of subjects with TEAEs within 14 days after each immunization will be summarized by severity and overall.

TEAE after each immunization will be summarized based on Safety Set for prime and boost immunization, respectively.

The following TEAEs will be listed by subject: related TEAEs, unrelated TEAEs, TEAEs leading to discontinuation, AESIs and SAEs.

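### The stated aim is comparability with the foreign data, but IgG is on a different scale, and solicited reactions over a different window, from the foreign figures the protocol quotes

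*Protocol*

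**What the plan says.** **Aim.** The Background and Rationale in Protocol Section 2.0 states that "the study is intended to confirm that the response (safety/immunogenicity) seen in foreign subjects is comparable to that in Chinese subjects". Section 4.2.6 repeats this, Sections 2.0 and 4.2.4 call the study a bridging trial, and both rationale sections tie the choice of the two doses to comparability with the German and US data. The formal objectives do not mention it. The primary objective (5.1.1) begins "To assess the safety and tolerability profiles of BNT162b1 prime/boost (P/B) immunization given 21 days apart" and refers only to Chinese subjects. The secondary objectives and SAP Section 3 contain no foreign comparison either.

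**IgG.** SAP 5.1 reports IgG as a titre: "Seronegative is defined as titers below the starting dilution (1:100) and assigned a titer of 50". The foreign results in Protocol 4.2.4.1 are concentrations: "geometric mean concentration (GMC) of RBD specific IgG was 534-1,778 U/mL 21 days after prime vaccination", and 7 days after the second dose "the GMC of RBD specific IgG antibody increased to 4,813-27,872 U/mL".

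**Reactions.** The foreign rates are 7-day rates: "Within 7 days of each vaccination, the most common systemic events reported in BNT162b1 and placebo groups were mild to moderate fatigue and headache", with injection-site pain reported over the same window. For each solicited reaction in this trial, SAP 7.6.1 says "the number and percentage of subjects with TEAEs within 14 days after each immunization will be summarized by severity and overall". The protocol synopsis promised more, with percentages "summarized by event severity for each day within 14 days after each vaccine/placebo vaccination and overall". Protocol 13.1.4 gives only the 14-day summary by severity. SAP 2.3 states that its analyses are consistent with the protocol.

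**The concern.** If a trial is justified as a bridge to foreign data, its tables should contain figures that can be read against those data. For IgG, a Chinese GMT numerically close to or far from the foreign figure would reflect the units as much as the population. For reactogenicity, a longer window can move the rate in one direction only, so the Chinese rates would look the same or worse by construction. The SAP expects its results to support regulatory submissions and publications, where a comparability sentence drawn from the rationale could be attached to figures that do not support it.

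**Working it through.** **1. The plan's own design figure.** Protocol 13.3 and SAP 4.3 give an 86.5% chance of at least one TEAE in 24 subjects at a rate of 8%. Check: 1 − 0.92^24 = 0.8648, so it reproduces. It concerns detection of one event and says nothing about comparability. The documents contain no comparability figure, margin or criterion.

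**2. IgG.** Let k be the unknown number of titre units per U/mL. The ratio of interest is GMT / (k × foreign GMC).
- Neither document gives k, a shared standard or a reference serum.
- For illustration, assume a GMT of 1,600 here and take the foreign 4,813 U/mL. With k = 0.05 the ratio is 1,600 / 240.65 = 6.65; with k = 2 it is 1,600 / 9,626 = 0.17. The values of k are assumptions. They show that the answer is set by k, not by the data.
- Abroad, the concentrations are quoted beside 38 convalescent samples with a GMC of 602 U/mL: 4,813 / 602 = 8.0 and 27,872 / 602 = 46.3. No counterpart ratio is planned here.
- Fold rise and seroconversion have no units but do not solve the problem. A seronegative subject's baseline is the assigned 50, so fold rise = titre / 50, and half that floor would double it. The documents quote no foreign fold rise or seroconversion rate.

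**3. Neutralising antibody.** Both programmes report a GMT. The foreign figures are for 21 days after the first dose (described only as a moderate increase) and 7 days after the second (168 to 267). Both times are planned here, at Visits 5 and 6. The protocol also reads the foreign values against convalescent serum: 168 / 94 = 1.79 and 267 / 94 = 2.84, matching its 1.8 to 2.8. The titres can be set side by side, with the caveat that neither document describes a shared control linking the assays.

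**4. Reaction window.** Let p7 be the 7-day rate and b the share of still-unaffected subjects with a first onset in days 8 to 14. Then p14 = p7 + (1 − p7) × b. The p7 values are US rates from Protocol 4.2.4.1; b is assumed.

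| Foreign 7-day rate | b = 0 | b = 5% | b = 10% |
|---|---|---|---|
| 75.0% (fever, 30 µg, dose 2) | 75.0% | 76.3% | 77.5% |
| 58.3% (pain, 10 µg, dose 1) | 58.3% | 60.4% | 62.5% |
| 8.3% (fever, 10 µg, dose 2) | 8.3% | 12.9% | 17.5% |

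Protocol 4.2.4.1 says that most foreign reactions peaked at 2 days and had resolved at day 7, which points to a small b. The shift is then minor for common reactions and larger, in relative terms, for rare ones.

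**5. Fever threshold.** Foreign fever is 38.0°C or above. This trial's main definition is axillary 37.3°C or above, which is 37.3 + 0.2 = 37.5°C oral by the conversion in Appendix B. The FDA grading of related reactions in SAP 7.6.1 partly covers this, since Appendix C starts at 38.0°C oral.

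**6. Precision once scales are aligned.** Take 24 subjects here against 12 abroad, the denominator of most quoted foreign rates.
- With identical observed rates, the Newcombe-Wilson 95% interval for the difference is about −26 to +31 points at 75% and −30 to +31 points at 58.3%.
- For a GMT ratio, the 95% limits are the ratio multiplied and divided by 10^(t × SD × √(1/24 + 1/12)), with t on 34 degrees of freedom. This factor is 1.39 at a log10 SD of 0.2 and 2.70 at 0.6. The SDs, and 12 foreign subjects with titres, are assumptions.

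Aligned outputs would therefore still support description rather than confirmation.

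**The case against.** The strongest reply is that comparability is background, not an objective. Sections 2.0 and 4.2.6 also state the objective as assessing safety and immunogenicity in Chinese subjects, the SAP plans no formal testing, and a descriptive phase I plan meets the objectives it lists. That stands. It limits the weight of the point, but the aim is still stated repeatedly and given as the reason for the doses.

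A reader might infer that the plan yields nothing that can be set beside the foreign results. The documents do not support that. Neutralising GMTs are titres at matching visits. The foreign adverse-event proportions have planned counterparts. The lymphocyte and neutrophil findings can be read against laboratory shift tables on the FDA scale. The rise with dose and after the boost can be checked within this trial in any unit.

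On reactions, SAP 7.6.1 follows Protocol 13.1.4; the by-day wording is in the synopsis only, so the protocol itself is not uniform. SAP 7.1.2 defines onset time from the corresponding immunisation, and 7.6.1 plans a distribution of occurrence for TEAEs. Neither is specified as a 7-day rate for each reaction, so the table is still missing. Because daily diaries are collected (Protocol 9.3.4), nothing is lost.

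The laboratory manual, Investigator's Brochure and mock-up tables were not available and may describe calibration or further tables. Even so, the SAP text specifies no calibrated IgG output.

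**Conclusion.** The concern holds in limited form. As planned, IgG GMTs cannot be compared numerically with the foreign U/mL values; the size of the scale difference is unknown because no conversion is given. The 14-day reaction rates can only equal or exceed the 7-day rates in the same subjects. The excess is probably small for common reactions (75.0% to 76.3% if 5% of unaffected subjects have late onset) and larger in relative terms for rare ones (8.3% to 12.9%). Those shifts rest on an assumed late-onset share.

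It would be tempting to conclude that the trial cannot show comparability because of its units and window. That goes too far for neutralising antibody, adverse events and laboratory data, and the window problem is recoverable. It also misses the more basic gap: no foreign comparison or criterion is planned, so aligned scales alone would not confirm comparability. The point is worth correcting because the remedy is cheap. It does not threaten the listed objectives.

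**What to change.** 1. **SAP 7.6.1.** Add a table of each solicited reaction within 7 days of each dose, by grade on the NMPA scale and the FDA scale already planned. State how the day of vaccination is counted: Protocol 10.2.1 includes it in the 14 days, and SAP 7.1.2 gives it an onset time of zero. Restore the by-day summary from the synopsis. All of this comes from diary data already collected. The cost is SAP wording and a few extra tables.

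2. **Protocol 2.0 and 4.2.6.** Restate the aim as a descriptive comparison with the foreign data. Say that IgG titres are not to be compared numerically with foreign U/mL values unless a common reference has been run in both assays, and that neutralising GMTs are set beside the foreign values without a shared control. The cost is a narrower stated conclusion.

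Running a convalescent panel here is not the recommended route. The documents describe no such sera, it would need extra assays, and a panel other than the 38 foreign samples would not be a common reference.
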